6.0 SCHEDULE OF ASSESSMENTS

Procedure	Prestudy	Screening	Day 1 of each Cycle ¹ (unless otherwise noted)	End of TX	Response Follow-Up (q 3mo±7 days) Until Progression
Informed consent	Х	Х			
Medical History	Х				
Physical Examination	Х	Х	Х	Х	Х
Toxicity (adverse events)		from time of procurement	Х	х	
Concomitant medications		Х	Х	х	х
Performance Status		Х	X	Х	Х
Radiological Tumor Assessment (chest/abdomen/pelvis)		within 4 weeks (must be post- procurement)	every 6 weeks ± 7 days from Cycle 1	Within 45 days	х
CBC with differential	X ²	Х	Х	Х	Х
HIV testing, if applicable		Х			
Hepatitis testing, if applicable		Х			
Serum Chemistry	X ³	Х	Х	Х	Х
PBMC collection for Immune Function Analysis	≤ 1 week of tumor procurement	х	Cycles 2, 4, and 6 Day 1prior to chemotherapy administration	х	3 months post EOT and q 6 months thereafter
Plasma collection for ctDNA	≤ 1 week of tumor procurement	Х	(Cycles 2, 3, 4, and 6 Day 1 prior to chemotherapy administration	х	
Pregnancy Test (if applicable)		Х			
Vigil administration			Day 15 q 21±3 days⁴		
depending on randomization			Day 15 y 2115 uays		
Injection Site Assessment			Day 16 only (may be conducted at home) ⁵		
Temozolomide			Days 1 – 5, q21 days		
Irinotecan			Days 1 – 5, q21 days		

¹ Subjects who are stable at the end of Cycle 4, with prior approval by the Sponsor may conduct evaluations on Day 15 of each cycle (1 Cycle = $21 \text{ days } \pm 3 \text{ days}$)

² Obtain from medical records from standard preoperative hematology and chemistry panels.

³ Obtain from medical records from standard preoperative hematology and chemistry panels.

⁴ Cross-over subjects will receive Vigil on Day 1

⁵ Cross-over subjects will have assessment on Day 2

Procedure	Prestudy	Screening	Day 1 of each Cycle ¹ (unless otherwise noted)	End of TX	Response Follow-Up (q 3mo±7 days) Until Progression
Survival Status	х				Long Term Follow Up ⁶
Immunohistochemistry		X ⁷			

7.0 SAMPLE SIZE JUSTIFICATION

This is an open label randomized controlled Phase III clinical trial. Information concerning the predicted survival of the control group is limited, based on rarity of disease and few published reports. However expert advisors in the EWS field estimate a conservative one-year survival rate of 25% in the chemotherapy control group. The one-year survival rate of 60% in the Vigil treated group is estimated from EWS patients treated on the Vigil phase 1 protocol. These estimates correspond to a hazard ratio (HR) of 0.383 favoring Vigil over control.

Assuming 1:1 randomization and the use of a two-sided log rank test at the alpha=0.0476 level of significance, 67 events will provide 90% power to detect an PFS HR of 0.45. Assuming a Group B (control group) median PFS of 6 months, a one-year accrual period, and a six-month follow-up period after randomization of the last subject, it is estimated that the total sample size (number of subjects) required to achieve 67 events is 114 (57 patients in each arm).

An unblinded interim analysis will be conducted by an independent data monitoring committee (IDMC) when 40 PFS events have occurred. Based on the results of this interim analysis, the planned sample size may be increased to 120 events. If the sample size is increased to 120 events, then the study will have approximately 90% power to detect a true HR of 0.55. Note that if the sample size is increased to 120 events, then the accrual period will be extended to 24 months, with a 6-month follow-up period after randomization of the last patient. Under these assumptions, it is estimated that approximately 164 patients will need to be randomized in order to achieve 120 events. Section 16.6 provides further details.

7.1 Definition of Progression Free Survival (PFS)

- Progression free survival (PFS) is defined as the time from randomization to the event of disease recurrence/progression or death due to any cause.
- Radiographic disease recurrence/progression will be assessed using the RECIST 1.1 criteria. If the disease recurrence/progression assessment involves more than one date, the earliest date will be used as the event date.

⁶ After progression, subjects will be contacted by phone quarterly for documentation of survival status.

⁷ These slides should correlate with tumor procured for vaccine manufacture.

- Patients who are alive and recurrence free at the time of analysis data cut-off, or who terminate the study for reasons other than disease progression or death, or who receive non-protocol treatment for Ewing's Sarcoma, will be censored on the last assessment date at which a RECIST 1.1 evaluation of disease status was made.
- Patients missing baseline disease assessment will be censored at date of randomization.
- For equivocal findings of recurrence (e.g., very small and uncertain new lesions; cystic changes or necrosis in existing lesions), treatment may continue until the next scheduled assessment. If recurrence is confirmed at the next scheduled assessment, the date of recurrence should be the earlier date when recurrence was suspected.

8.0 ANALYSIS POPULATIONS

The intent-to-treat (ITT) population will include all randomized subjects. All efficacy analyses will be completed in the ITT population.

The Safety population will include all patients who receive study treatment and patients will be analyzed according to actual treatment received. All safety analyses will be completed in the Safety population.

8.1 Efficacy Analyses

8.1.1 Primary Efficacy Analysis

The primary endpoint of PFS is the time from randomization to progression according to RECIST version 1.1 or death. The distributions of PFS in the two arms will be compared using a two-sided log-rank test at the alpha=0.0476 level of significance.

8.1.2 Secondary Efficacy Analyses

A fixed sequence testing procedure will be used to control the overall level of significance for the analysis of the secondary endpoints of OS and ORR. If the primary analysis of PFS is statistically significant (p<0.0476), then OS will be analyzed using a two-sided test at the alpha=0.0476 level of significance. In addition, if the analysis of OS is statistically significant (p<00476), then ORR will be analyzed using a two-sided test at the alpha=0.0476 level of significance. However, if an earlier analysis is not statistically significant, the remaining analyses will be exploratory rather than confirmatory.

The secondary endpoint of OS is defined as time from randomization to death or to the date of last follow-up. The date of last follow-up confirming survival will be used as the censoring date for subjects who are alive and/or do not have a known date of death. The analysis of OS will be conducted using the log rank test. Kaplan-Meier OS curves will be displayed by treatment arm. Median OS and percent OS at fixed time points will be estimated.

The secondary endpoint of ORR will be analyzed using Pearson's chi-square test. Overall response rate (ORR) is defined as the proportion of patients who have prolonged stable disease or a partial or complete response to therapy according to RECIST 1.1. ORR will be reviewed 6 months after treatment with Vigil.

The secondary analysis of all secondary endpoints will be conducted using two-sided tests at the alpha=0.05 level of significance.

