8.4.1 Schedule, Dose and Administration

	Drug	Dose	Schedule	
	Temozolomide 100 mg/m ² daily, oral		Days 1 – 5, every 21 days	
Group A	Irinotecan 50 mg/m ² daily, oral		Days 1 – 5, every 21 days	
	Vigil	1.0 x 10 ⁶ cells/injection, intradermal	Day 15, every 21 days	

Cross-Over	Drug	Dose	Schedule
Subjects	Vigil	1.0 x 10 ⁶ cells/injection, intradermal	every 21 days

Subjects will receive Vigil at 1.0×10^6 cells via intradermal injection **every 3 weeks for a minimum of 4 administrations to** a maximum of 12 administrations depending on quantity of Vigil manufactured from surgical specimens and so long as the patient is clinically stable and without disease progression.

The sites of injection for Vigil will be rotated between the right and left upper arms. If the ipsilateral axillary lymph nodes were radiated or surgically removed during prior therapy, alternative sites may be used.

	Drug	Dose	Schedule
Group B Temozolomide		100 mg/m² daily, oral	Days 1 – 5, every 21 days
	Irinotecan	50 mg/m² daily, oral	Days 1 – 5, every 21 days

Please contact the sponsor with any dose adjustment considerations.

Irinotecan Preparation

Order the injectable formulation of irinotecan from central supplier, Clinigen. Draw up 1 cycle of (five doses) into provided oral syringes and dispense to the subject with instructions to refrigerate until administration. Irinotecan may be mixed with cranberry-grape juice before administration to mask the bitter flavor and administered once daily on Days 1 through 5 of each 3-week cycle.

Temozolomide Preparation

Temozolomide capsules for 1 cycle will be obtained by the patient with administration instructions. Temozolomide may be opened and mixed in apple sauce or juice if unable to swallow whole capsules. Temozolomide is administered on Days 1 through 5 of each 3-week course and given at least 1 hour before irinotecan.

Subjects should be instructed to complete a dosing diary for the administration of oral irinotecan and oral temozolomide.

Premedications and post medications

Vigil: EMLA® may be utilized at the injection site prior to Vigil administration. Analgesics may be employed as necessary. As noted above, systemic steroids or other immunosuppressants should be avoided due to immune inhibition activity.

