- 8. Serum chemistries (creatinine, glucose, total protein, blood urea nitrogen (BUN), total carbon dioxide (CO2), albumin, total bilirubin, alkaline phosphatase, and aspartate transaminase (AST) and/or alanine transaminase (ALT)) and electrolytes (total calcium, chloride, potassium, sodium) must be performed.
- 9. Blood collection for immune function analysis (ELISPOT).
- 10. Plasma collection for immune function analysis (ctDNA).
- 11. Pregnancy test for those of childbearing potential.
- 12. Submission to Gradalis, Inc. of preferably 20 unstained tumor slides or tissue block for correlative immunohistochemistry assay. These slides should correlate with tumor procured for vaccine manufacture.

Assessments During Treatment

The following evaluations will be performed on Day 1 of each cycle (1 Cycle = 21 days \pm 3 days) (unless otherwise specified):

- 1. *A physical examination, including vital signs and body weight.
- 2. *A toxicity assessment (CTCAE v 5).
- 3. *Assessment of concomitant medications.
- 4. Radiological assessment of disease status with CT chest /abd/pelvis (MRI abd/pelvis may be substituted for CT abd/pelvis) every 6 weeks ± 7 days from Cycle 1 regardless of treatment arm assignment or treatment delay. The methods used for prestudy assessments (e.g., CT or MRI) should be used throughout the study. If possible, the same equipment should be used each time.
- 5. *A CBC with differential and platelet count.
- 6. *Serum chemistries (creatinine, glucose, total protein, blood urea nitrogen (BUN), total carbon dioxide (CO2), albumin, total bilirubin, alkaline phosphatase, and aspartate transaminase (AST) and/or alanine transaminase (ALT)) and electrolytes (total calcium, chloride, potassium, sodium).
- 7. Blood collection for immune function analysis (ELISPOT) on Day 1 (prior to chemotherapy administration) at Cycles 2, 4, and 6.
- 8. Plasma collection for immune function analysis (ctDNA) on Day 1 prior to chemotherapy administration at Cycles 2, 3, 4 and 6.
- 9. *Assessment of Karnofsky Performance Status or LS.
- 10. Group A and B participants: oral temozolomide 100 mg/m² daily (Days 1 5, total dose 500 mg/m²/cycle)
- 11. Group A and B participants: oral irinotecan 50 mg/m² daily (Days 1 5, total dose 250mg/m²/cycle)
- 12. Group A participants: Vigil 1.0 x 10⁶ cells/injection, intradermally on Day 15.
- 13. Cross-over Subjects: Vigil 1.0 x 10⁶ cells/injection, intradermally every 21 days

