10.0 CROSS-OVER

Subjects randomized to Group B may cross-over to Group A after discussion with, and approval from the Gradalis medical monitor or authorized designee.

Within 6 weeks of second relapse or progression and if alternative therapy has not been given since EOT, subjects randomized to Group B, will be allowed to cross-over to receive single agent Vigil every 21 days following End of Treatment assessment. Subjects who cross-over may receive up to 12 doses of Vigil depending upon the quantity of Vigil manufactured. After the Group B EOT assessment, the subject will start "cross-over" from Assessments During Treatment onward. Vigil and all assessments will occur on Day 1 of each cycle.

Cross-over must occur within 2 years of End of Treatment assessments of Group B enrollment. Subjects who progress \geq 8 weeks post EOT assessment must re-screen and if they qualify will start "cross-over" from Assessments During Treatment onward. Eligibility criteria for cross-over subjects are listed below.

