16.4.2 Secondary Efficacy Analyses

A fixed sequence testing procedure will be used to control the overall level of significance for the analysis of the secondary endpoints of OS and ORR. If the primary analysis of PFS is statistically significant (p<0.0476), then OS will be analyzed using a two-sided test at the alpha=0.0476 level of significance. In addition, if the analysis of OS is statistically significant (p<00476), then ORR will be analyzed using a two-sided test at the alpha=0.0476 level of significance. However, if an earlier analysis is not statistically significant, the remaining analyses will be exploratory rather than confirmatory.

The secondary endpoint of OS is defined as time from randomization to death or to the date of last follow-up. The date of last follow-up confirming survival will be used as the censoring date for subjects who are alive and/or do not have a known date of death. The analysis of OS will be conducted using the two-sided log-rank test. Kaplan-Meier OS curves will be displayed by treatment arm. Median OS and percent OS at fixed time points will be estimated.

The secondary endpoint of ORR will be analyzed using Pearson's chi-square test. Overall response rate (ORR) is defined as the proportion of patients who have a partial or complete response to therapy according to RECIST 1.1. ORR will be reviewed 6 months after treatment with Vigil.

The analyses of all other secondary endpoints will be conducted using two-sided tests at the alpha=0.05 level of significance.

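### The SAP's ORR counts prolonged stable disease and the protocol's does not, and both documents time its review from Vigil, which Group B does not receive as randomised

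*SAP*

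**What the plan says.** Protocol 16.4.2 defines ORR as the "proportion of patients who have a partial or complete response to therapy according to RECIST 1.1". SAP 8.1.2 defines it as the "proportion of patients who have prolonged stable disease or a partial or complete response to therapy according to RECIST 1.1". The SAP does not say how long stable disease must last to count. Elsewhere (abbreviation list and section 3.2) the SAP calls the same quantity the objective response rate by RECIST 1.1.

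Both sections carry the same timing sentence: "ORR will be reviewed 6 months after treatment with Vigil". Neither says whether the six months run from the first or the last dose.

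Vigil as randomised treatment belongs to one arm. Protocol 9.0 lists "Group A participants: Vigil 1.0 x 10⁶ cells/injection, intradermally on Day 15". For the other arm, Protocol 10.0 says that after second relapse or progression "subjects randomized to Group B, will be allowed to cross-over to receive single agent Vigil every 21 days".

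The status of the test is stated in SAP 8.1.2: "A fixed sequence testing procedure will be used to control the overall level of significance for the analysis of the secondary endpoints". If PFS and then OS are significant, "then ORR will be analyzed using a two-sided test at the alpha=0.0476 level of significance". The test is Pearson's chi-square, and SAP 8.0 places all efficacy analyses in the ITT population, so both arms enter it.

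**The concern.** A confirmatory test needs one endpoint, fixed in advance and measurable in the same way in both arms. ORR fails this in two ways.

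- **What counts.** Stable disease is not an objective response under RECIST. Adding it turns the quantity into a disease-control rate that still carries the ORR label. Because the duration is unstated and the trial is open label, a cut-off would have to be set later, possibly with outcomes visible. Prolonged stability also largely repeats what PFS already measures, namely the absence of progression.
- **When it is assessed.** A review time counted from Vigil has no meaning for a Group B patient who never crosses over. For one who does, it falls after progression on the randomised treatment.

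At stake is the third confirmatory claim: the same data could support it under one document and not under the other.

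**Working it through.** **1. The plan's own figures.** Neither document gives an ORR rate, power or sample size. The stated size rests on PFS and reproduces: events = 4(z for two-sided 0.0476 + z for 90% power)² / (ln 0.45)² = 4(1.981 + 1.282)² / 0.638 ≈ 67. With a control median of 6 months, 12 months of accrual and 6 of follow-up, 114 patients give 67.5 expected events. The ORR definition changes none of this.

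**2. The definitions side by side.**

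| | Protocol 16.4.2 | SAP 8.1.2 |
|---|---|---|
| CR, PR | count | count |
| Prolonged stable disease | does not count | counts, duration not given |
| Label | ORR, RECIST 1.1 | ORR, RECIST 1.1 |
| Review time | 6 months after Vigil | 6 months after Vigil |

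The sponsor's own usage agrees with the protocol. The Figure 9 legend in Protocol 2.3 reports a Phase I ORR of 12.5% from one NED and one PR, i.e. 2/16. Protocol 3.0 and SAP 2.0 list a prolonged stable disease separately from the responses.

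**3. Can the definition change the test?** Assumed counts, 57 per arm (Protocol 16.1), Pearson chi-square without continuity correction: χ² = N(ad − bc)² / [(a+b)(c+d)(a+c)(b+d)].

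| CR+PR / prolonged SD / other | CR+PR only | With SD added |
|---|---|---|
| A 20/12/25, B 16/4/37 | 20 vs 16: χ² = 0.65, p = 0.42 | 32 vs 20: χ² = 5.09, p = 0.024 |
| A 28/6/23, B 17/17/23 | 28 vs 17: χ² = 4.44, p = 0.035 | 34 vs 34: χ² = 0, p = 1.00 |

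The result can switch in either direction at 0.0476.

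**4. Power under assumed rates** (57 per arm, two-sided 0.0476, normal approximation, B vs A):

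- CR+PR 30% vs 50%: 58%.
- Plus SD 20% in both arms (50% vs 70%): 58%.
- Plus SD 10% in B and 20% in A (40% vs 70%): 90%.
- Plus SD 20% in B and 10% in A (50% vs 60%): 18%.

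The definition matters to the extent that stable disease differs between the arms.

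**5. The review time.** Protocol 8.4.1 gives Vigil every 3 weeks from a minimum of 4 doses to "a maximum of 12 administrations depending on quantity of Vigil manufactured from surgical specimens". With dose 1 on Day 15, dose k falls on Day 15 + 21(k − 1): dose 4 on Day 78, dose 12 on Day 246. Adding 183 days:

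- from dose 1: Day 198, about week 28;
- from a fourth and last dose: Day 261, about week 37;
- from a twelfth: Day 429, about week 61.

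The anchor is therefore ambiguous by up to 33 weeks (61 − 28) within Group A, and undefined in Group B. With the assumed control median PFS of 6 months, more than half of Group B would be expected to have progressed or died by even the earliest of these dates.

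**The case against.** The best reply is that the protocol definition is complete on which responses count, and that the SAP's objective and abbreviation list agree with it, so one stray SAP phrase is out of line. The timing sentence says only that ORR is reviewed then, not that later or earlier responses are ignored. Imaging every 6 weeks from Cycle 1 regardless of arm (Protocol 9.0) already supplies comparable data. ORR is reached only if PFS and OS both succeed. When stable disease is equally common in both arms, the definition barely affects power, and the reversals above come from constructed tables with a marked imbalance.

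Much of this is fair. It limits the consequence and makes the protocol definition the natural one to keep. It does not settle the conflict: no text gives the protocol precedence, and an analyst following the SAP would test the wider quantity. Nor does it supply a review time for Group B, which an ITT comparison of two arms requires whichever definition is used.

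The sponsor's seven earlier combination-treated patients are weak evidence of size. Their rate moves from 3/7 = 43% (2/7 = 29% if the CR seen at autopsy is not a RECIST response) to 4/7 = 57%. The step from 43% to 57% is one patient, there is no comparator, and all seven had already failed this chemotherapy. The figures illustrate the shift and do not estimate it.

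**Conclusion.** The concern holds. The two documents define different endpoints for the same confirmatory test, and the shared review time cannot be applied to Group B as randomised. On identical data the choice of definition can move the result across 0.0476 in either direction (0.42 to 0.024, or 0.035 to 1.00). Those p-values and the power range of 18% to 90% rest on assumed counts and rates, since the documents give none for ORR. The conflict itself rests only on the text. PFS, OS, the 67 events and the 114 patients are unaffected, and the confirmatory consequence arises only if the first two tests succeed.

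**What to change.** 1. In SAP 8.1.2, remove prolonged stable disease from the definition, so that both documents define ORR as a best overall response of CR or PR by RECIST 1.1 in the ITT population.
2. In Protocol 16.4.2 and SAP 8.1.2, replace the sentence timed from Vigil with one clock for both arms. A workable choice is best response from randomisation to the first of progression, non-protocol therapy or cross-over. The existing 6-weekly imaging supports it, and responses after cross-over stay out of the comparison.
3. If disease control is of interest, name it as a separate exploratory endpoint outside the fixed sequence, with a minimum duration stated now.
4. In the same edit, settle two neighbouring points: SAP 4.2 and 8.1.2 also put the secondary analyses at alpha 0.05, against 0.0476 in the sequence, and SAP 12.1 provides for local and central readings without saying which determines response.

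The cost is SAP wording and one protocol sentence. No new data are needed and the sample size does not change. The reported rate may be lower than under the current SAP definition.

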8.1.3 Sensitivity Analyses of the Primary Endpoint

Five sensitivity analyses of the primary endpoint will be conducted using each of the following modifications to the definition of PFS:

- If the disease recurrence/progression assessment involves more than one date, the latest date will be used as the event date.
- If disease recurrence or death occurs right after missing data for a scheduled radiographic disease assessment (including missing the assessment or assessment results in an unevaluable status for overall response per RECIST 1.1), the patient will be censored at the date of the last radiographic disease assessment.
- If a patient receives non-protocol treatment for Ewing's Sarcoma, the patient will be treated as having progression at the date of the last radiographic disease assessment.
- Patients missing baseline disease assessment will be treated as having progression at the date of randomization.
- For equivocal findings of recurrence (e.g., very small and uncertain new lesions; cystic changes or necrosis in existing lesions) for whom treatment continues until the next scheduled assessment, and if recurrence is confirmed at the next scheduled assessment, the date of recurrence should be the earlier date when recurrence was suspected.

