16.4.3 Sensitivity Analyses of the Primary Endpoint

Five sensitivity analyses of the primary endpoint will be conducted using each of the following modifications to the definition of PFS:

- If the disease recurrence/progression assessment involves more than one date, the latest date will be used as the event date.
- If disease recurrence or death occurs right after missing data for a scheduled radiographic disease assessment (including missing the assessment or assessment results in an unevaluable status for overall response per RECIST 1.1), the patient will be censored at the date of the last radiographic disease assessment.
- If a patient receives non-protocol treatment for Ewing's Sarcoma, the patient will be treated as having progression at the date of the last radiographic disease assessment.
- Patients missing baseline disease assessment will be treating as had having progression at the date of randomization.
- For equivocal findings of recurrence (e.g., very small and uncertain new lesions; cystic changes or necrosis in existing lesions) for whom treatment continues until the next scheduled assessment, and if recurrence is confirmed at the next scheduled assessment, the date of recurrence should be the date when recurrence was confirmed.

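### The fifth PFS sensitivity analysis in the SAP uses the primary dating rule for equivocal progression, so it cannot differ from the primary result, and it conflicts with the protocol

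*SAP*

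**What the plan says.** **Primary rule.** SAP 7.1, on equivocal findings: "If recurrence is confirmed at the next scheduled assessment, the date of recurrence should be the earlier date when recurrence was suspected". Protocol 16.2 sets the same rule.

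**Sensitivity analyses in the SAP.** SAP 8.1.3 opens: "Five sensitivity analyses of the primary endpoint will be conducted using each of the following modifications to the definition of PFS". Its fifth bullet concerns equivocal findings in patients whose treatment goes on to the next planned assessment and whose recurrence is confirmed there, and ends: "the date of recurrence should be the earlier date when recurrence was suspected".

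**Sensitivity analyses in the protocol.** Protocol 16.4.3 lists the same five analyses. Its fifth bullet has the same lead-in but ends: "the date of recurrence should be the date when recurrence was confirmed".

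**Scan schedule.** Protocol Section 9.0 places on-treatment imaging every 6 weeks, within 7 days either way, counted from Cycle 1. The quarterly schedule applies after the study agent is discontinued.

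**Who reads the images.** Protocol 12.1 sends images for third-party review, and SAP 12.1 plans both local and central assessment. Neither document says which reading supplies the dates for the primary analysis.

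**The concern.** A sensitivity analysis of an event date is informative only if it uses a different date. Here the primary rule backdates a confirmed equivocal finding to the scan on which it was first suspected. The natural check is to date it at confirmation instead and see whether the treatment comparison moves. The protocol plans that check; the SAP replaces it with the primary rule.

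Two things follow. Anyone programming from the SAP will produce an analysis that agrees with the primary by construction, and the analysis promised in the protocol will not be done. If the slip is noticed only after results are known, restoring the protocol's rule will look like a choice made with the data in view.

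Whether a small or uncertain change counts as equivocal is a judgement, and the trial is open label, so the question deserves a working check.

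**Working it through.** **Step 1. The three dating rules side by side.**

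| Place | Role | Date given to a confirmed equivocal finding |
|---|---|---|
| SAP 7.1 (and protocol 16.2) | primary | suspected (earlier) |
| SAP 8.1.3, fifth bullet | sensitivity | suspected (earlier) |
| Protocol 16.4.3, fifth bullet | sensitivity | confirmed (later) |

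The closing clause of SAP 7.1 and that of the fifth bullet of SAP 8.1.3 match word for word, apart from one capital letter. Between the fifth bullets of the SAP and the protocol there are two differences: the SAP adds the word for the earlier date, and it has suspicion where the protocol has confirmation.

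**Step 2. Does the lead-in rescue the SAP analysis?** The primary rule says that treatment may continue; the fifth bullet is limited to patients whose treatment does continue. Patients inside that group get the suspected date, as in the primary analysis. Patients outside it are not touched by the bullet and keep the primary definition. Every event date is unchanged, so the difference in Z and in HR is exactly 0 in any dataset.

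**Step 3. Reproduce the plan's own figure.** SAP 7.0 states: "67 events will provide 90% power to detect an PFS HR of 0.45". Inputs from SAP 7.0 are two-sided alpha 0.0476, 1:1 allocation and 90% power. Schoenfeld's formula is

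d = 4 (z₁₋α/₂ + z₁₋β)² / (ln HR)²

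= 4 (1.981 + 1.282)² / (ln 0.45)² ≈ 42.6 / 0.638 ≈ 66.8, so 67 events.

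Power at 67 events is 90.1%. With exponential PFS, a 6-month control median, 12 months of uniform accrual and 6 months of follow-up, 114 subjects give 67.5 expected events. The plan's figures reproduce. They do not depend on the fifth bullet.

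**Step 4. Shift per affected event under the protocol's rule.** One on-treatment scan interval is 42 days. In months that is 42 / 30.4375 = 1.38, or 1.38 / 6 = 23% of the assumed control median. This is the shift of a single event date, not the effect on the result.

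**Step 5. Effect on the result.** The share of progressions that start as equivocal is not in the documents, so 10% to 30% per arm is assumed. Setup: 57 patients per arm, true HR 0.45, the accrual and follow-up of step 3, scans every 6 weeks, every equivocal progression confirmed one scan later, administrative censoring only, 400 simulated trials per row. Negative changes in Z favour Vigil.

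| Equivocal share, Vigil / control | Mean change in Z | Mean absolute change in Z | HR, primary → confirmation date |
|---|---|---|---|
| 10% / 10% | 0.006 | 0.035 | 0.434 → 0.434 |
| 20% / 20% | 0.002 | 0.048 | 0.425 → 0.426 |
| 30% / 30% | 0.000 | 0.054 | 0.433 → 0.433 |
| 30% / 10% | −0.079 | 0.085 | 0.424 → 0.415 |
| 10% / 30% | +0.087 | 0.089 | 0.447 → 0.458 |

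Repeating the analysis under the SAP's fifth bullet gave a change in Z of exactly 0 in every simulated trial.

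**The case against.** The strongest reply is that this is a transcription slip in one supportive analysis, that the protocol already holds the intended rule, and that the numerical effect is small. All of that stands, and it limits the weight of the point. It does not remove it: the SAP is the document that directs the programming, and the two current texts disagree.

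Other replies:

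- **Overlap with the first sensitivity analysis.** That analysis takes the latest date when an assessment involves several. It might reach pairs of suspected and confirmed dates, but the SAP does not say so, and both documents list the equivocal case as a separate item.
- **Central review.** Third-party reading may reduce the dependence on local judgement. Because the documents do not say which reading drives the primary analysis, the concern is reduced but not removed.

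A reader might also infer more than the documents support:

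- **That the missing check would have tested pseudo-progression.** Protocol 7.1 does discuss apparent early growth under immunotherapy, but for patients treated on after RECIST progression has been called. The fifth bullet concerns equivocal findings that are later confirmed. If apparent progression resolves, neither version of the bullet applies.
- **That events could move by 3 months.** The bullet is limited to patients whose treatment continues, so the 6-week on-treatment schedule is the relevant one.
- **That the identical result will be presented as evidence of robustness.** The SAP does not say how sensitivity results will be interpreted, and a result that matches the primary in every digit might well be noticed as an error.

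**Conclusion.** The point holds as an error in the SAP text. The fifth analysis equals the primary analysis by construction, four of the five listed modifications are real, and the SAP conflicts with protocol 16.4.3. These conclusions rest on the wording alone and need no assumption.

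The size of what is lost does rest on an assumption, namely that 10% to 30% of progressions per arm start as equivocal. In that range the protocol's analysis would change Z by about 0.04 to 0.05 on average with equal shares, and by about 0.08 to 0.09 with shares of 30% and 10% in either direction. Against a critical value of 1.981, that could change a conclusion only in a borderline result.

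It would be wrong to infer that the primary PFS result is in doubt. The primary definition, the log-rank test at 0.0476, the 67 events and the other four sensitivity analyses do not depend on this bullet.

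**What to change.** In SAP 8.1.3, fifth bullet, replace the closing clause, "the date of recurrence should be the earlier date when recurrence was suspected", with the protocol's: "the date of recurrence should be the date when recurrence was confirmed". The lead-in can stay as it is, since it already matches protocol 16.4.3.

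The cost is one line in the SAP. Both dates come from scheduled scans, so no new data are needed, and the sample size and alpha do not change. The correction should be made before the sponsor sees unblinded results, so that the restored analysis counts as prespecified.
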